9.3.1 Analysis Endpoints

Primary

Progression Free Survival (PFS) per RECIST 1.1

Progression Free Survival is defined as the time from initiation of definitive therapy to the first documented disease progression per RECIST 1.1 based on radiologists' review or death due to any cause, whichever occurs first, or last patient follow-up that documented lack of disease progression. Patients who have not had disease progression or who have died, will be censored on the most recent clinical evaluation date that documented that they were progression-free.

Secondary

Overall Survival

Overall Survival (OS) is defined as the time from initiation of definitive therapy to death due to any cause or last patient contact alive. Subjects without documented death at the time of the final analysis will be censored at the date of the last follow-up.

Toxicity Determination

Tolerability of therapy will be determined on the basis of CTCAE adverse event reporting. Toxicity will be reported separately for definitive therapy and Pembrolizumab. For the definitive therapy phase, we will report on adverse events which are grade 3 or higher treatment-related toxicities or any grade of pneumonitis or esophagitis. For the Pembrolizumab phase, we will report all treatment-related toxicities.

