Treatment with Pembrolizumab will continue for 17 cycles (about 12 months) in the absence of (1) documented disease progression, (2) unacceptable adverse event(s), (3) intercurrent illness that prevents further administration of treatment, (4) investigator's decision to withdraw the subject, (5) subject withdrawal of consent, (6) pregnancy of the subject, (7) noncompliance with trial treatment or procedure requirements, (8) institution of alternative systemic treatment, or (9) other administrative reasons. After the end of treatment, each subject will be followed for a minimum of 30 days for adverse event monitoring (serious adverse events will be collected for up to 90 days after the end of treatment). Subjects will have post-treatment follow-up for disease status until one of the following events: (1) disease progression; (2) initiation of non-study cancer treatment; (3) withdrawal of study consent; (4) loss to follow-up or (5) death. In addition, survival status beyond the establishment of PD or initiation of subsequent therapies will be documented.

The primary objective of the trial includes determination of PFS per RECIST 1.1. Secondary objectives include OS and safety/toxicity determination as assessed by a variety of parameters of adverse events (AEs), including incidence and time to first Grade 3-5 AE. Pre-specified adverse events of clinical interest during the Pembrolizumab phase include the following events: 1) Grade \geq 3 diarrhea 2) Grade \geq 2 colitis, 3) Grade \geq 2 pneumonitis, 4) Grade \geq 3 hypo- or hyperthyroidism, 5) Grade \geq 2 hypophysitis, 6) Grade \geq 2 uveitis, and 7) Grade \geq 2 nephritis. Participation in this trial will encourage supplying tumor tissue from either a newly obtained formalin-fixed specimen (preferred) or an older formalin-fixed, paraffin-embedded specimen, from locations not radiated prior to biopsy. The specimen will be evaluated at a central laboratory facility for expression status of PD-L1 in a retrospective manner. Eligibility for the trial will not be dependent upon PD-L1 expression status, but the sponsor may amend the trial in the future if new data arise regarding the predictive value of PD-L1 expression. Any patient enrolled on the study prior to such an amendment, however, will remain on study.

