3.2 Primary Study Endpoints

The primary endpoint is PFS, which measures the length of time from the first day of proton reirradiation +/- concurrent chemoradiation until progressive disease, death from any cause, or last patient contact.

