5.5.2 Prohibited Concomitant Medications

Subjects are prohibited from receiving the following therapies during the Pre-Pembrolizumab Screening and Pembrolizumab Treatment Phase of this trial:

- Anti-cancer systemic chemotherapy or biological therapy
- Immunotherapy not specified in this protocol
- Investigational agents other than Pembrolizumab
- Radiation therapy
 - Note: Radiation therapy to a symptomatic solitary lesion or to the brain may be allowed after consultation with Sponsor, but would be regarded as a disease progression event for the primary outcome.
- Live vaccines within 30 days prior to the first dose of trial treatment and while participating in the trial. Examples of live vaccines include, but are not limited to, the following: measles, mumps, rubella, chicken pox, yellow fever, rabies, BCG, and typhoid (oral) vaccine. Seasonal

Phase II Pembrolizumab Reirradiation

influenza vaccines for injection are generally killed virus vaccines and are allowed; however intranasal influenza vaccines (e.g. Flu-Mist®) are live attenuated vaccines and are not allowed.

- Glucocorticoids for any purpose other than an abbreviated course to modulate symptoms from an event of clinical interest of suspected immunologic etiology. The use of physiologic replacement doses of corticosteroids may be approved after consultation with the Sponsor.

Subjects who, in the assessment by the investigator, require the use of any of the aforementioned treatments for clinical management should be removed from the trial. Subjects may receive other medications that the investigator deems to be medically necessary.

There are no prohibited therapies during the Post-Treatment Follow-up Phase.

5.6 *Rescue Medications and Supportive Care*

5.6.1 *Supportive Care Guidelines*

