8.1.2.6 Tumor Imaging and Assessment of Disease

The initial tumor imaging will be performed within 42 days prior to the first day of proton reirradiation or as indicated according to standard of care. Scans performed as part of routine clinical management are acceptable for use as the screening scan if they are of diagnostic quality and performed within 30 days prior to the first day of treatment. Tumor imaging will be repeated at the conclusion of chemoradiation and within approximately 30 days prior to the first dose of pembrolizumab. Imaging while on pembrolizumab will be performed every 12 weeks (1 day before Pembrolizumab up until the day of the next infusion) after the first dose of pembrolizumab or more frequently if clinically indicated. Tumor imaging timing should follow calendar days and should not be adjusted for delays in cycle starts or extension of Pembrolizumab cycle frequencies. This image schedule will also be adjusted per subject's insurance coverage.

For patients that receive at least one dose of Pembrolizumab, after the first documentation of progression (if the subject is clinically stable) confirmatory scans may be performed as early as 28 days later; alternately, the scan performed at the next scheduled time point (e.g. every 84 ± 7 days) may be used as confirmation.

After the first documentation of progression, it is at the discretion of the investigator either to verify true PD, to keep a clinically stable subject on trial treatment or to stop trial treatment until repeat imaging performed at least 28 days later confirms progression. Clinical Stability is defined as:

- 1) Absence of symptoms and signs indicating clinical significant progression of disease (including worsening of laboratory values) indicating disease progression.
- 2) No decline in ECOG performance status.
- 3) Absence of rapid progression of disease or progressive tumor at critical anatomical sites (e.g., cord compression) requiring urgent alternative medical intervention.

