9.4 Statistical Methods

Primary Objective

1. The primary intent-to-treat analysis will estimate progression free survival from initiation of definitive therapy by the Kaplan-Meier method. Median PFS and 95% CI will be determined. A total of 41 patients will be enrolled on the study.
2. A secondary proof of principle analysis will determine the clinical benefit of adding consolidation Pembrolizumab after definitive therapy. Only patients who receive consolidation Pembrolizumab are included in this analysis. It is expected that up to 15% of enrolled patients will have progressive disease or lingering toxicity and will not start Pembrolizumab after definitive therapy. Thus we anticipate that at least 35 patients will be included.

In this proof of principle analysis, we will compare progression free survival from initiation of definitive therapy to a historical control value. We assume the median PFS for the historical control population treated with standard therapy only is 6 months and the median PFS for the patients treated with definitive therapy and consolidation Pembrolizumab is 10 months. Assuming 35 patients are enrolled over 2 years and followed for an additional 3 months, the final analysis will have 80% power to detect an improvement in median PFS assuming exponential survival and 1-sided 5% significance level.

Secondary Objectives

1. Overall survival will be estimated by the Kaplan-Meier method. Median OS and 95% CI will be determined.
2. Toxicities will be graded, categorized and tabled. For the definitive therapy phase, we will report on adverse events which are grade 3 or higher treatment-related toxicities or any grade of pneumonitis or esophagitis. For the Pembrolizumab phase, we will report all treatment-related toxicities.

Exploratory Objective

1. Biomarkers will be tested for association with PFS using log rank test for categorical biomarkers and Cox proportional hazards regression for continuous biomarkers. Biomarkers will be tested for association with graded toxicity (i.e., worse toxicity grade) for specific categories of toxicity using chi square test for categorical biomarkers and Spearman's correlation for continuous biomarkers.

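### The PFS censoring sentence in section 9.3.1, as worded, censors patients who have died, although the definition just before it counts death from any cause as an event

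*Combined protocol and SAP*

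**What the plan says.** Three statements on PFS bear on this point.

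- **Definition, section 9.3.1.** PFS runs from the start of definitive therapy to first documented RECIST 1.1 progression "or death due to any cause, whichever occurs first, or last patient follow-up that documented lack of disease progression".
- **Censoring sentence, section 9.3.1, immediately after.** "Patients who have not had disease progression or who have died, will be censored on the most recent clinical evaluation date that documented" them to be progression-free.
- **Protocol body, section 3.2.** PFS is measured "until progressive disease, death from any cause, or last patient contact".

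The overall survival rule in section 9.3.1 is worded as one would expect: "Subjects without documented death at the time of the final analysis will be censored at the date of the last follow-up".

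Section 9.4 gives the two analyses that use PFS. The primary one is a Kaplan-Meier estimate in all 41 patients, with a median and 95% CI and no test. The secondary one compares patients who received pembrolizumab with a fixed historical median of 6 months: "Assuming 35 patients are enrolled over 2 years and followed for an additional 3 months, the final analysis will have 80% power" to detect a median of 10 months, one-sided 5%, exponential survival. Section 9.4 adds no censoring rule of its own.

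**The concern.** One death cannot be both an event and a censored observation. A programmer who works from the definition counts it. One who works from the censoring sentence, which is the part that looks like an operational rule, does not.

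The error would run in one direction only. Dropping deaths without progression from the event count can only make PFS look longer. The trial has a single arm judged against a fixed historical value, so no control group carries the same error to offset it. If the wording is settled only after data are seen, the choice between two written rules that give different medians becomes post hoc.

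There is also a smaller mismatch over the censoring date. Section 3.2 runs to last patient contact, and section 9.3.1 to the last evaluation that documented no progression. A contact without a disease assessment gives the later date.

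**Working it through.** **1. The passages side by side**

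| Place | Death without progression | Censoring date |
|---|---|---|
| 9.3.1, PFS definition | Event | Last follow-up showing no progression |
| 9.3.1, PFS censoring sentence | Censored, as worded | Last evaluation showing no progression |
| 3.2 | Ends PFS | Last patient contact |
| 9.3.1, overall survival | Event | Last follow-up |

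Only the censoring sentence departs from the others on deaths, and no other section repairs it.

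**2. The plan's own figure**

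Inputs from section 9.4: 35 patients, 24 months of accrual, 3 months of further follow-up, medians 6 and 10 months, one-sided 5%, exponential. Uniform accrual is assumed. With λ = ln 2 / median, the probability that a patient has an event by the analysis is

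P = 1 − [exp(−3λ) − exp(−27λ)] / (24λ).

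- Median 6: λ = 0.1155, P = 1 − (0.7071 − 0.0442)/2.7726 = 0.761, so 35 × 0.761 = 26.6 events.
- Median 10: λ = 0.0693, P = 1 − (0.8123 − 0.1539)/1.6636 = 0.604, so 35 × 0.604 = 21.1 events.

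Log-hazard test, with null variance for the critical value and alternative variance for the spread:

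power = Φ{[ln(10/6) − 1.645/√26.6] × √21.1} = Φ{(0.511 − 0.319) × 4.60} = Φ(0.883) = 81%.

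Other standard approximations and simulation mostly fall between 76% and 83%. The stated 80% is therefore reproduced with every progression and every death counted as an event. The rewording restores that assumption and changes no design figure.

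**3. Size of the error under the literal reading (illustration)**

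Assumption: a share q of PFS events are deaths without progression. The documents do not give q, so 5%, 10% and 20% are used.

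If deaths were censored on the day they occurred, the apparent hazard would be (1 − q)λ and the apparent median would be the true median/(1 − q). For a true median of 6 months this gives 6/0.95 = 6.3, 6/0.90 = 6.7 and 6/0.80 = 7.5 months.

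The sentence censors earlier than the day of death, at the last evaluation before it. Simulation with that rule used the scan schedule of section 8.1.2.6. Reirradiation lasts 3 to 8 weeks, with a scan at its end; pembrolizumab starts 4 to 12 weeks later, with one scan in the 30 days before it ("Tumor imaging will be repeated at the conclusion of chemoradiation and within approximately 30 days prior to the first dose of pembrolizumab"); scans then follow every 12 weeks. The schedule was applied to all patients, as a simplification. Delay in detecting progression between scans was not modelled.

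For 41 patients with a true median of 6 months, expected events are 41 × 0.761 = 31.2.

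| q | Deaths censored (31.2 × q) | Kaplan-Meier median, true 6 | Kaplan-Meier median, true 10 |
|---|---|---|---|
| 0 | 0 | 6.0 | 10.0 |
| 5% | 1.6 | 6.3 | 10.5 |
| 10% | 3.1 | 6.6 | 11.0 |
| 20% | 6.2 | 7.3 | 12.3 |

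**4. The 35-patient comparison**

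Section 9.4 names no test. With an assumed one-sample log-rank test and a true median of 6 months, the same simulation rejects in about 4% of trials at q = 0, and in about 6%, 10% and 21% at q = 5%, 10% and 20%. These rates leave out a feature of the real subgroup, taken up under the objection.

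**The case against.** The strongest reply is that this is a slip nobody would act on. The negation can be read as covering both clauses, so that the sentence means patients who have neither progressed nor died. The definition directly above it and section 3.2 both count death. Taken with full literalness, the sentence would even censor patients who progressed first and died later, which is absurd. All of this stands as evidence of intent. It does not make the sentence correct: the repeated relative pronoun works against the benign parse, and this is the only place where the PFS censoring rule is spelled out.

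A reader might infer three stronger things that the documents do not support.

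- **That the plan intends an endpoint in which deaths are censored.** The definition, section 3.2 and the overall survival sentence all point the other way.
- **That the 35-patient test would have a false-positive rate of up to 21%.** That figure needs the literal reading, an assumed share of deaths and an assumed test. It also ignores section 8.1.5.3, under which patients must be free of progression before pembrolizumab, while PFS is counted from the start of definitive therapy. Adding the condition of being event-free at the start of pembrolizumab gives about 71% rejection with no deaths censored at all. That figure is itself only indicative, because the model loses about a third of patients early against the up to 15% expected in section 9.4. The 4% baseline therefore does not describe the subgroup as selected.
- **That the plan leaves open whether progression or death after new anticancer therapy counts.** By its plain terms section 9.3.1 counts the first documented progression or any death, with no exception for new therapy. What is uneven is follow-up. Section 3.1 ends disease follow-up at "1) disease progression; (2) initiation of non-study cancer treatment", among other events, and sections 5.8 and 8.1.1.5.3 are similar. Section 8.1.2.6 has such a stop only for patients who discontinue for reasons other than progression. Sections 4.4.1, 4.4.2, 8.1.5.5 and 8.1.5.7 state no such stop. Likewise, section 5.5.2 already settles permitted radiotherapy ("but would be regarded as a disease progression event for the primary outcome"), so its absence from section 9.3.1 is a missing cross-reference and not a gap.

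**Conclusion.** The censoring sentence in section 9.3.1 is wrong as written and should be corrected before analysis. It contradicts the definition beside it, on the primary endpoint. The likely cause is a dropped negation, so this is a drafting error and not a different estimand.

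If it were applied literally, the primary 41-patient median would be overstated by about 0.3, 0.6 or 1.3 months on a true 6 months. This rests on exponential PFS, the section 8.1.2.6 scan schedule, and an assumed 5%, 10% or 20% of events being deaths without progression. The direction does not depend on those assumptions; the size does. The rejection rates for the 35-patient comparison should not be presented as expected harm.

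**What to change.** **Needed**

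- Section 9.3.1: replace the censoring sentence with: Patients who have neither progressed nor died will be censored on the most recent evaluation date that documented that they were progression-free.
- Section 3.2: replace the last-contact wording with the same censoring date.

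The cost is one sentence and one phrase. No extra scans are needed, and sample size, significance level and stated power are unchanged. PFS will read shorter than under the literal rule, because that rule overstates it.

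**Optional housekeeping, not part of the error**

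- Cross-reference the section 5.5.2 radiotherapy rule in section 9.3.1.
- Reconcile the sections that stop disease follow-up at new anticancer therapy (3.1, 5.8, 8.1.1.5.3, and 8.1.2.6 for patients who discontinue for reasons other than progression) with those that state no such stop. If they were reconciled towards continued disease follow-up, some imaging beyond what section 8.1.2.6 now requires could be needed.

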7 TRIAL FLOW CHART

7.1 Trial Flow Chart

Table 6: Study procedures by visit

Trial Period:	Screening Phase	Proton Reirradiation +/- Chemo-therapy	Pembrolizumab Treatment Cycles*										Post-Treatment	
Treatment Cycle /Title:	Screening	Reirradiation	1/9	2/10	3/11	4/12	5/13	6/14	7/15	8/16	17	Safety Follow-up	Follow Up Visits	
Scheduling Window (Days):	-28 to -1	Daily protons for 3-8 weeks	± 3	± 3	± 3	± 3	± 3	± 3	± 3	± 3	At last treatment	30 days post tx/discon	Every 3 months for 2 yrs	
Administrative Procedures														
Informed Consent	X													
Inclusion/Exclusion Criteria	X													
Demographics and Medical History	X													
Prior and Concomitant Medication Review	X	X	X	X	X	X	X	X	X	X	X			
Trial Treatment Administration			X	X	X	X	X	X	X	X	X			
Post-study anticancer therapy status												X		X
Survival Status		X	X	X	X	X	X	X	X	X	X	X		X
Clinical Procedures/Assessments														
Review Adverse Events**			X	X	X	X	X	X	X	X	X	X		X
Full Physical Examination	X					X				X		X		X
Directed Physical Examination		X	X	X	X		X	X	X		X			
Vital Signs and Weight	X	X	X	X	X	X	X	X	X	X	X	X		X
ECOG Performance Status	X	X	X	X	X	X	X	X	X	X	X	X		X
Laboratory Procedures/Assessments: analysis performed by LOCAL laboratory														
Pregnancy Test – Urine or Serum β-HCG	X													
PT/INR and aPTT	X													
CBC with Differential	X			X	X	X	X	X	X	X	X	X		X
Comprehensive Serum Chemistry	X			X	X	X	X	X	X	X	X	X		X

Phase II Pembrolizumab Reirradiation

Trial Period:	Screening Phase	Proton Reirradiation +/- Chemo-therapy	Pembrolizumab Treatment Cycles*										Post-Treatment	
			Pembrolizumab Treatment Cycles*										Post-Treatment	
Treatment Cycle /Title:	Screening	Reirradiation	1/9	2/10	3/11	4/12	5/13	6/14	7/15	8/16	17		Safety Follow-up	Follow Up Visits
Scheduling Window (Days):	-28 to -1	Daily protons for 3-8 weeks	± 3	± 3	± 3	± 3	± 3	± 3	± 3	± 3	At last treatment	30 days post tx/discon	Every 3 months for 2 yrs	
Urinalysis	X				X				X			X		
T3, FT4 and TSH	X			X			X			X		X		
Efficacy Measurements														
Tumor Imaging	X***	X	X				X, X				X			X
Tumor Biopsies/Archival Tissue Collection/Correlative Blood Studies														
Archival or Newly Obtained Tissue Collection (optional)	X													
Correlative Studies Blood Collection	X			X				X			X	X	X	

For the Pembrolizumab phase, we will report all treatment-related toxicities.

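### The PFS censoring date in 9.3.1 does not require a scan, so pembrolizumab visits without imaging can be credited as progression-free time, which pushes the PFS median modestly upward

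*Combined protocol and SAP*

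**What the plan says.** Section 9.3.1 defines PFS as the "time from initiation of definitive therapy to the first documented disease progression per RECIST 1.1 based on" the radiologists' review, or death from any cause if that comes first. Patients without an event "will be censored on the most recent clinical evaluation date that documented that they were progression-free". Section 3.2 gives a second end point for the same variable: the patient's last contact, with no condition on disease status.

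Section 8.1.2.6 sets the scan schedule: "Imaging while on pembrolizumab will be performed every 12 weeks" after the first dose, more often if clinically indicated, and adjustable to insurance coverage. Section 3.1 requires directed imaging for new signs or symptoms and puts the pembrolizumab cycles about 21 days apart. Table 6 (section 7.1) lists examination, vital signs and ECOG status under "Clinical Procedures/Assessments" at each cycle. Tumor imaging is in a separate block for efficacy measurements.

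Section 5.5.2 adds one more event type: permitted radiation to a symptomatic lesion or the brain is treated as progression for the primary outcome.

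Section 9.4 uses this PFS variable twice: for the primary intention-to-treat Kaplan-Meier median, and for the secondary comparison with a historical median of 6 months.

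**The concern.** The two halves of the definition apply different standards of evidence. Progression needs a scan read by a radiologist; being progression-free needs, on its face, only a clinical evaluation. During pembrolizumab about three cycle visits fall between consecutive scheduled scans. An examination cannot establish absence of RECIST progression, yet under the plain reading it moves the censoring date forward. A progression already present but not yet imaged waits for the next scan, while the patient's event-free time keeps growing visit by visit.

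The number of events is the same under either censoring date. Only the follow-up of censored patients changes, and only upward. At stake are the primary Kaplan-Meier median and the secondary test, which is where the plan says the benefit of adding pembrolizumab will be determined. With about 35 patients and no control arm, nothing else in the design offsets such a shift.

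**Working it through.** **1. The plan's own figure.** Inputs from 9.4: "We assume the median PFS for the historical control population treated with standard therapy only is 6 months"; "the median PFS for the patients treated with definitive therapy and consolidation Pembrolizumab is 10 months"; 35 patients, 24 months' accrual, 3 months' further follow-up; "assuming exponential survival and 1-sided 5% significance level".

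With uniform accrual, P(event) = 1 − (e^(−3λ) − e^(−27λ)) / (24λ), where λ = ln 2 / median.
- Median 10: 1 − (0.812 − 0.154)/1.664 = 0.604; × 35 = 21.1 events.
- Median 6: 1 − (0.707 − 0.044)/2.773 = 0.761; × 35 = 26.6 events.
- Power = Φ[(ln(10/6) − 1.645/√26.6) × √21.1] = Φ[(0.511 − 0.319) × 4.60] = Φ(0.88) = 0.81.

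The plan says "the final analysis will have 80% power to detect an improvement in median PFS", so its figure is reproduced. It assumes exactly observed event times.

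**2. Simulation of the two censoring dates.** 35 patients, 3,000 trials per scenario, exponential PFS.
- From the documents: reirradiation 3–8 weeks; gap to pembrolizumab 4–12 weeks; scans at the end of reirradiation, within about 30 days before the first dose, every 12 weeks on drug (up to 3 weeks late, except in D), then 3-monthly; visits every 3 weeks for 17 cycles, a 30-day safety visit, then visits together with scans.
- Assumed: uniform timing within those windows; the share of events seen at once; dropout; every patient starts pembrolizumab.
- Test assumed, because 9.4 names none: one-sample log-rank z = (E − O)/√E, with E = (ln 2 / 6) × total months of follow-up, rejecting above 1.645. On exactly observed times it rejects in 3.8% of trials at a true median of 6.

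Each pair below is last-scan censoring → last-visit censoring.

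| Scenario | Mean gap, visit minus scan (true 6 / true 10) | KM median, true 6 | KM median, true 10 | Rejection, true 6 |
|---|---|---|---|---|
| A: 10% of events are deaths seen at once | 4.70 / 3.95 wk | 7.32 → 7.55 | 11.03 → 11.51 | 11.2% → 16.3% |
| B: A, plus 30% found at once by directed imaging | 4.53 / 3.90 wk | 6.93 → 7.16 | 10.66 → 11.17 | 6.6% → 10.2% |
| C: A, plus dropout of 0.6% per week | 4.15 / 3.98 wk | 7.20 → 7.53 | 10.81 → 11.51 | 9.3% → 16.8% |
| D: nothing seen early, scans exactly on time | 4.25 / 3.68 wk | 7.37 → 7.60 | 11.18 → 11.66 | 12.9% → 18.8% |

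- Gap: 3.68/4.35 = 0.85 month to 4.70/4.35 = 1.08 months.
- Rise in median: 0.23 month at true 6 and 0.48 to 0.51 at true 10 without dropout; 0.33 and 0.70 with it. Large-sample values for A: 6.89 → 7.08 and 10.80 → 11.29.
- Rise in rejection: 5.1, 3.6, 7.5 and 5.9 points for A to D.

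**3. Hand check of A at true median 6.** On average 9.8 of 35 patients are censored, so O = 25.2. The exponential estimate under scan censoring is 6.88 months, so E is about 25.2 × 6.88/6 = 28.9 and z is about (28.9 − 25.2)/√28.9 = 0.69. Visit censoring adds 9.8 × 1.08 × 0.1155 = 1.2 to E, giving z of about (30.1 − 25.2)/√30.1 = 0.89. A shift of about 0.2 in z with O unchanged agrees with the table.

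**4. Splitting the excess.** In A, late detection at scans takes rejection from 3.8% to 11.2% (7.4 points) and the censoring date adds 5.1. In B the two parts are 2.8 and 3.6 points.

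**5. Steadiness.** Other simulations with 35 patients and the same assumed 40% seen at once gave about 8% → 11% and 9.3% → 13.5%. The increment, about 3 to 4 points in that case, is steadier than the level, which depends on the form of the statistic and on simulation detail.

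**The case against.** The strongest reply is textual. The rule asks for an evaluation that documented progression-free status, under an endpoint headed as PFS per RECIST 1.1. If a visit without imaging cannot document that, it does not qualify, and the censoring date becomes the last scanned visit. This stands as a permissible reading, so the text is ambiguous rather than plainly wrong. It does not dispose of the point: the sentence names a clinical evaluation, 3.2 asks only for contact, and an analyst could choose between the readings after seeing the data.

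A reader might infer that PFS events can be dated only by scans 12 weeks apart. The documents do not support that. Death counts in the same sentence, new signs or symptoms trigger directed imaging (3.1), there is imaging at the end of reirradiation and before pembrolizumab (8.1.2.6), and permitted radiation counts as progression (5.5.2). A visit that raises suspicion therefore leads to a scan. Scenario B allows for early detection; the bias shrinks but does not vanish.

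The gap arises mainly on pembrolizumab, since follow-up visits and imaging are both about 3-monthly. That limits its reach, but with 24 months' accrual and 3 months' follow-up most censored patients are still in that phase: 66% (true median 10) to 78% (true median 6) in simulation had not passed their last scheduled cycle at the cut.

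Finally, the primary analysis only estimates a median, and the shift is small beside its sampling error. With 41 patients the standard deviation of the median is about 1.3 months (true 6) and 2.5 months (true 10), so the shift is about 0.2/1.3 = 0.15 to 0.5/2.5 = 0.20 of a standard deviation. This is fair as to size. Unlike sampling error, however, the shift has a fixed direction.

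**Conclusion.** The point holds as a modest weakness in a stated primary-endpoint rule. Section 9.3.1 lets an evaluation without imaging set the censoring date, and 3.2 is looser. If such visits are used, each censored patient gains about one unassessed month on average. The Kaplan-Meier median rises by about 0.2 to 0.5 month (up to 0.7 with the assumed dropout), and rejection at a true 6-month median rises by about 4 to 8 points. The direction was upward in every scenario run. The sizes depend on the assumed share of events seen at once (0 to 40%), on dropout, and on the assumed test.

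Three stronger conclusions do not follow. First, the plan does not establish that PFS will be overstated; that depends on which reading is applied. Second, the full false-positive excess in the table cannot be charged to the censoring rule, because much of it is late detection at scans. Third, the comparison with 6 months need not always favour the regimen: the documents do not say how progression was dated or patients censored in the historical figure.

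**What to change.** In 9.3.1, replace the clinical evaluation date with the date of the last tumor imaging assessment read as showing no RECIST 1.1 progression, or day 1 of reirradiation if there is none. Amend 3.2 so that it gives the same end date. Keep censoring at the last clinical visit as a named sensitivity analysis, so that readers can see how far the choice moves the median and the secondary test.

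The cost is one sentence in each section. Scan dates are already collected, so no new data or visits are needed. The reported median will be slightly less favourable, and under the same assumptions rejection at a true 10-month median falls a little (scenario A: 92.9% to 88.9%; B: 86.8% to 82.2%). The change does not address late detection at scans, which should be acknowledged separately when the result is set against 6 months.
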